6.4.6. Laboratory Parameters

Baseline values and values at each visit for each laboratory parameter collected will be descriptively summarized.

Laboratory data will also be summarized using shift tables where appropriate. Each patient's continuous laboratory safety parameter values will be flagged as "low", "normal", "high" or "missing" relative to the normal ranges. Each patient's categorical laboratory safety parameter values will be flagged as "abnormal" or "normal". This categorical data will be summarized in shift tables comparing the minimum post-baseline value, maximum post-baseline value and all other relevant post-baseline visits with those at the baseline visit. Note that minimum post-baseline will only be displayed in the instances where there is a range with $LLN > 0$.

In addition, CTCAE grade and hyperphosphatemia grade will be summarized. Shift tables of grade from baseline to maximum or minimum on-treatment as applicable will be produced. This analysis will also be produced considering cycle 1 only.

Laboratory results will be included in by-patient listings and will include CTCAE grade and hyperphosphatemia grade at each visit, as well as change from baseline at each visit.

Hy's law

Subjects who have elevated ALT, AST, and total bilirubin post baseline will be summarized descriptively as follows and Hy's law cases identified.

- ALT and AST: $> 3x$ Upper Limit of Normal (ULN), $> 5x$ ULN, $> 10x$ ULN, $> 20x$ ULN
- Total bilirubin $> 2x$ ULN
- ALT or AST: $> 3x$ ULN and Total bilirubin $> 2x$ ULN

Plots of ALT and AST vs. Total bilirubin by module will also be produced with reference lines at $3 \times ULN$ for ALT, AST, and $2 \times ULN$ for total bilirubin. In each plot, peak total bilirubin $\times ULN$ will be on the vertical axis and peak ALT or AST $\times ULN$ will be on the horizontal axis.

6.4.7. Evaluation of Performance Status

ECOG performance status will be summarized in a shift table, which will summarise values at baseline, each visit and the maximum values during the study.

All ECOG performance assessments will be provided in a by-patient listing.

6.5. PK/PD Analysis

PK analyses are not the responsibility of [REDACTED] and details of planned analyses will be covered in a separate statistical analysis plan.

6.6. PRO Assessments (Substudies 1, 3, 4 and 5)

All PRO assessments analyses will be performed using the safety/ITT population and presented per substudy and cohort.

6.6.1. Establishing the Minimally Important Clinical Difference

For each assessment the minimally important difference (MID) in a score at C3D1 and C5D1 will be determined following the recent protocol by the EORTC Quality of Life Group ([Musoro 2018](#)). The Global Self Evaluated Transition (G-SET™) is a single item questionnaire administered twice during the study after 6 weeks (at C3D1) and 12 weeks (at C5D1). The questionnaire is a patient-rated change in health between two time periods using a five point ordinal scale (1 = much better now than 6 weeks ago; 2 = somewhat better now than 6 weeks ago, 3 = about the same as 6 weeks ago; 4 = somewhat worse now than 6 weeks ago; 5 = much worse now than 6 weeks ago).

Patients with complete data will be categorized into five mutually exclusive clinical change groups (CCG) reflecting the five possible levels of change. For each pair of timepoints (Change in summary score from baseline at C3D1 and Change in summary score from C3D1 at C5D1), a patient can thus belong to only one CCG category. Two methods for determining the MID will be explored:

1. Mean Change Method

For a given mean absolute change in PRO assessment scale summary score: the MID for improvement is equal to the mean summary score of the 'small positive change' CCG (somewhat better now than 6 weeks ago) and the MID for deterioration is equal to the mean summary score of the 'small negative change' CCG (somewhat worse now than 6 weeks ago). The mean summary score of the 'small change' CCGs and that of the 'no change' CCG will be compared and reported. If the mean summary score for 'no change' CCG is similar to any of the two 'small change' CCGs, the estimated MID may be considered doubtful. No a priori rule will be established to determine if mean summary scores are sufficiently similar to determine MID to be doubtful.

2. Linear Regression

For a given absolute change in PRO assessment scale summary score: the estimate of the numerical change in summary score that is associated with the transition between adjacent CCG categories will be determined using linear regression. Separate models will be fitted for improving and deteriorating scores based on the anchor. The outcome variable is the PRO assessment summary score, and the covariate is a binary anchor variable; coded as 'no change'=0 and 'small positive change'=1 for model on improvement (Other CCG categories are excluded from the linear regression model), and 'no change'=0 and 'small negative change'=1 for model on deterioration (Other CCG categories are excluded from the linear regression model). The resulting β 's (i.e. slope parameters) correspond to the MIDs for improvement and deterioration respectively. No other covariates will be included in these models.

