2.2 Secondary objectives

- To evaluate the efficacy of the study drugs as measured by disease control rate (DCR), duration of response (DOR), PFS and overall survival (OS)
- To assess the safety and tolerability of the study drugs
- To characterize the PK profile of derazantinib 200 mg BID (and, if applicable, derazantinib metabolites) as monotherapy (Substudy 5) and in combination with atezolizumab (Substudy 3).

- To evaluate changes, and assess the minimally important difference, in health-related quality of life (HR-QoL) and symptom response from baseline by cohort, substudy and in the overall study population using the EORTC QLQ C30, FACT-BI, EQ-5D (5L) visual analogue scale (VAS), and Health Transition Index/G-SET.

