Each scale will be summarized at each visit as a continuous variable using descriptive statistics per substudy and cohort for the total scores, change from baseline and percent change from baseline for all visits where the EORTC QLQ-C30 is collected. In addition, at C5D1, the change from C3D1 at C5D1 and the percentage change at C5D1 from C3D1 will also be reported. For each of the functional scales, the minimally important change from baseline at C3D1 and change from C3D1 at C5D1 will be determined using the two methods detailed in Section 6.6.1.

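### SAP 6.6.1 contradicts itself on whether the PRO minimally important difference is computed from score changes or score levels, and the SAP drops the overall-population and non-functional-scale MIDs without listing either

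*SAP*

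**What the plan says.** G-SET asks patients at C3D1 and C5D1 how their health compares with six weeks before. SAP 6.6.1 sorts patients with complete data into five change groups on that answer and explores two ways of deriving an MID.

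- **Mean Change Method.** "the MID for improvement is equal to the mean summary score of the 'small positive change' CCG", with a parallel sentence for deterioration. A check then compares the mean summary score of the no-change group with those of the two small-change groups; similar values make the MID doubtful.
- **Linear regression.** "The outcome variable is the PRO assessment summary score, and the covariate is a binary anchor variable", contrasting the no-change group with one small-change group. "No other covariates will be included in these models".

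Elsewhere the same section speaks of change. The first method's title does, both lead-ins do, and the time pairs are defined as change from baseline to C3D1 and from C3D1 to C5D1. The regression is said to deliver "the estimate of the numerical change in summary score that is associated with the transition between adjacent CCG categories". SAP 6.6.2, 6.6.3 and 6.6.4 call the result a minimally important change.

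On scope, SAP 6.6 states: "All PRO assessments analyses will be performed using the safety/ITT population and presented per substudy and cohort". Protocol 2.2 asks for changes and the MID in HR-QoL and "symptom response from baseline by cohort, substudy and in the overall study population". SAP 2.2 repeats the objective without that breakdown. For the QLQ-C30, SAP 6.6.3 says "For each of the functional scales, the minimally important change from baseline at C3D1" and the later interval will be determined, whereas Protocol 8.3.8 names the QLQ-C30 scales without restriction. SAP 6.8 lists only the dropped IPCW analysis as a change from the protocol.

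**The concern.** The anchor measures change over six weeks, so the quantity set against it has to be the change in score over the same six weeks. The contradiction falls on the outcome variable, in the sentences a programmer would implement.

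The two literal errors differ in kind. A mean-method MID of 53 or 67 on a 0–100 scale would probably be noticed. A level-based regression slope looks like a plausible MID and might pass unnoticed, even though it mixes the change of interest with whatever difference the anchor groups already had at baseline.

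The omissions are a separate matter. Without a pooled analysis, every MID rests on one cohort split into five anchor groups. Without global health status and the symptom scales, the QLQ-C30 scale closest in content to the global anchor has no MID, and neither do the scales behind the symptom response named in the objective.

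**Working it through.** The documents give no precision or sample size for the MID, so there is no stated figure to reproduce.

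**1. Mean method, literal reading.** Assume a typical score of 60 and true mean changes of +7 and -7.
- Score level: 60 + 7 = 67 for improvement; 60 - 7 = 53 for deterioration.
- Signed change: +7 and -7.

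The literal deterioration value is wrong in size and in sign.

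**2. Regression, literal reading.** With one binary covariate, the slope is the difference in group means:

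level slope = (difference in mean change) + (difference in mean baseline).

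- Equal baselines: the slope has the same expectation as regression on change.
- Illustration with opposing baselines: somewhat-better patients go from 60 to 68 and about-the-same patients stay at 70. Regression on change gives 8 - 0 = +8; regression on level gives 68 - 70 = -2.

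The sign reverses in expectation only when the opposing baseline gap exceeds the true difference in change.

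**3. Reading of absolute change.** Both lead-ins use the word absolute without defining it. If it meant unsigned change, a group with zero mean change would still show SD × √(2/π). With SD of change 20 this is 16.0; with 15.5 it is 12.4.

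**4. Cohort sizes.** From SAP 6.1.6, the Stage 2 totals are 74 + 36 + 50 + 50 + 26 = 236 and the Stage 1 totals are 35 + 18 + 16 + 16 + 13 = 98. These count evaluable patients; PRO analyses use the safety/ITT set, which may be somewhat larger.

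**5. Precision of the regression MID.** Assumptions, none in the documents: score SD 20 on a 0–100 scale; correlation ρ between time points 0.5–0.7; 60–80% of patients with complete data; 15–25% of those in a given small-change group and 40% in the no-change group.

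SE(change) = 20 × √(2(1-ρ)) × √(1/n_small + 1/n_none); half-width = 1.96 × SE.

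Example, N = 26, 80% complete, 25% small-change, ρ = 0.5: n_small = 26 × 0.8 × 0.25 = 5.2 and n_none = 26 × 0.8 × 0.4 = 8.3. SE = 20 × √(1/5.2 + 1/8.3) = 11.2, half-width 21.9.

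Ranges over the assumptions, with the outcome correctly set to change:

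| Analysis set | Small-change group | 95% half-width | Wrong sign, true difference 5 | Wrong sign, true difference 10 |
|---|---|---|---|---|
| One cohort, N 26–74 | 2–15 | 10–30 | 17–37% | 3–26% |
| Pooled, all stop at Stage 1, N 98 | 9–20 | 9–16 | 13–26% | 1–10% |
| Pooled, all complete, N 236 | 21–47 | 5.6–10 | 4–16% | 0–2% |

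Wrong-sign chance = Φ(-difference/SE).

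**6. Level regression under the same assumptions**, SE(level) = 20 × √(1/n_small + 1/n_none).
- Equal baselines: wrong-sign chance per cohort 23–37% (true difference 5) or 7–26% (10), close to the change-based figures.
- Opposing baseline gap of 10, true difference 5: the expected slope is 5 - 10 = -5. The wrong-sign chance is 63–77% per cohort, 74–81% pooled at 98 and 84–91% pooled at 236. More patients make it worse, because the bias stays while the noise shrinks.

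**7. Scope.** SAP Table 9 lists global health status, functional scales and symptom scales/items as separate blocks, so limiting the MID to functional scales excludes the other two. SAP 6.6.4 repeats the functional-scales wording for FACT-Bl, where no such block exists; functional well-being is only one of its five subscales.

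**The case against.** A reader might infer that the SAP plans a level-based MID and will therefore report wrong-signed values. The documents do not support that. The title, lead-ins, time pairs, stated regression target and later sections all point to change, and summary score after each lead-in can be read as shorthand for the change just introduced. A competent programmer may well do the right thing.

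Nor is the regression wrong-signed by construction. That needs an opposing baseline difference, and the documents say nothing about whether improvers start lower. Some wrong-sign risk is small-sample noise, which remains after the wording is corrected.

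Cohort-wise MIDs are not an error either: Protocol 2.2 asks for them, and Protocol 8.3 summarises all endpoints by substudy and cohort. The protocol does not rank the pooled estimate above the others. The EQ-5D VAS is already covered by SAP 6.6.2.

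All of this stands. It narrows the point to a contradiction in an operative rule plus two unlisted departures from the protocol. It does not remove the contradiction, since the sentences that define the estimators still name the score.

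**Conclusion.** The point holds as an internal contradiction, with two protocol–SAP mismatches. Certain from the text: the operative sentences name the score and not its change; a literal mean-method MID for deterioration would be positive; the overall-population MID and the QLQ-C30 MIDs outside the functional scales are missing; and SAP 6.8 mentions neither omission. Conditional: bias or sign reversal in the regression depends on baseline differences between anchor groups.

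The precision ranges rest on the assumed SD, correlation, completion and anchor distribution. They show why the pooled analysis is worth restoring: a small-change group of roughly 2–15 patients in a fully enrolled cohort, against 21–47 pooled at 236 or 9–20 pooled at 98. The stakes are modest. The MID belongs to a secondary PRO objective, Protocol 8.3.8 makes PRO analysis primarily descriptive, and no response-rate test, stopping rule or dose decision uses it.

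**What to change.** - In SAP 6.6.1, define the outcome in both methods, and in the doubtful check, as the signed raw change in score from baseline to C3D1 and from C3D1 to C5D1. State that absolute means raw as opposed to percentage change, not unsigned change.
- Add an MID pooled across Substudies 1, 3, 4 and 5 alongside the substudy and cohort values, all with confidence intervals.
- In SAP 6.6.3, extend the MID to global health status and the symptom scales, with direction reversed for symptoms. In SAP 6.6.4, clarify that functional scales means all FACT-Bl scales.
- If any of this is deliberately not done, list it in SAP 6.8 with the reason.

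The cost is SAP wording and one pooled run on data already collected. The small downside is that pooling assumes patients use the anchor alike across treatment lines; the cohort values, kept as descriptive output, give a rough check on that.

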6.6.2. EQ-5D (5L)

The EQ-5D (5L) is a standardized instrument for use as a measure of health outcome. The five health state dimensions in this instrument include the following: mobility, self-care, usual activities, pain/discomfort, and anxiety/depression. Each dimension is rated on a five-point scale from 1 (no problem) to 5 (extreme

problem). The EQ-5D (5L) also includes a graded (0 to 100) vertical visual analog scale (VAS) on which the patient rates his or her general state of health at the time of the assessment.

The 5 questions will be summarized descriptively as categorical variables per substudy and cohort for all visits where the EQ-5D (5L) is collected. Each dimension and the VAS will be summarized as a continuous variable using descriptive statistics for the scores, change from baseline and percent change from baseline for all visits where the EQ-5D (5L) is collected. In addition, at C5D1, the change from C3D1 at C5D1 and the percentage change at C5D1 from C3D1 will also be reported. The minimally important change from baseline at C3D1 and change from C3D1 at C5D1 will be determined using the two methods detailed in Section 6.6.1. Missing scores will not be included in summary statistics and only subjects with both an observation at the specified visit and at baseline will be included in change from baseline summaries.

6.6.3. EORTC QLQ-C30

The EORTC QLQ-C30 was developed to assess the quality of life of cancer patients and is the most widely used cancer-specific HR-QoL instrument. It contains 30 items and measures five functional dimensions (physical (PF), role (RF), emotional (EF), cognitive (CF) and social (SF)), three symptom scales (fatigue, nausea/vomiting, and pain), six single symptom items (dyspnea, sleep disturbance, appetite loss, constipation, diarrhea and financial impact) and global health and quality of life. The global health and quality of life items uses a 7-point scale scoring from 1 (very poor) to 7 (excellent). The other items are scored on a 4-point scale from 1 (not at all) to 4 (very much). A high score for a functional scale represents a high/healthy level of functioning. A high score for the global health status represents a high QoL. However, a high score for a symptom scale/item represents a high level of symptomatology/problems. The scoring method is outlined in Table 9 and the following paragraphs.

Table 9: Scoring the QLQ-C30 version 3.0

	Scale	Number of items	Item range	Version 3.0 Item numbers	Function scales
Global health Status /QoL	QL	2	6	29, 30	
Functional Scales					
Physical functioning	PF	5	3	1 to 5	F
Role functioning	RF	2	3	6,7	F
Emotional functioning	EF	4	3	21 to 24	F
Cognitive functioning	CF	2	3	20, 25	F
Social function	SF	2	3	26, 27	F
Symptom scales/items					
Fatigue	FA	3	3	10, 12, 18	
Nausea and vomiting	NV	2	3	14,15	
Pain	PA	2	3	9, 19	
Dyspnea	DY	1	3	8	
Insomnia	SL	1	3	11	
Appetite loss	AP	1	3	13	
Constipation	CO	1	3	16	
Diarrhea	DI	1	3	17	
Financial difficulties	FI	1	3	28	

Raw score (RS) is calculated as the average of item score when at least half of the items are not missing. A linear transformation to 0–100 will then be applied to get the score (S) using the item range provided in Table 9.

For functional scales $S = (1-(RS-1)/range) \times 100$

For symptom scales/items and global health status $S = ((RS-1)/range) \times 100$

Each scale will be summarized at each visit as a continuous variable using descriptive statistics per substudy and cohort for the total scores, change from baseline and percent change from baseline for all visits where the EORTC QLQ-C30 is collected. In addition, at C5D1, the change from C3D1 at C5D1 and the percentage change at C5D1 from C3D1 will also be reported. For each of the functional scales, the minimally important change from baseline at C3D1 and change from C3D1 at C5D1 will be determined using the two methods detailed in Section 6.6.1.

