6.1.4. Handling of Dropouts and Missing Data

Unless indicated otherwise, summary statistics will be reported for observed data only and missing data will not be imputed. Patients whose clinical response is unknown or not reported will be treated as non-responders.

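### Percent change is planned for QLQ-C30 symptom scales whose best score is 0, so it is undefined for symptom-free patients and can contradict the absolute change in either direction

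*SAP*

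**What the plan says.** SAP 6.6.3 states the scope first: "Each scale will be summarized at each visit as a continuous variable using descriptive statistics per substudy and cohort". The quantities are the score, "change from baseline and percent change from baseline for all visits where the EORTC QLQ-C30 is collected". At C5D1 a second pair is added: "the change from C3D1 at C5D1 and the percentage change at C5D1 from C3D1 will also be reported". Table 9 of the SAP lists nine symptom scales and items (fatigue, nausea and vomiting, and pain as multi-item scales, plus six single items), so all nine are covered.

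On scoring, the symptom items run from 1 (not at all) to 4 (very much). Then: "A linear transformation to 0–100 will then be applied to get the score (S) using the item range provided in Table 9". The direction is explicit: "a high score for a symptom scale/item represents a high level of symptomatology/problems".

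Neither document gives a rule for a zero denominator. The general rule in SAP 6.1.4 is that, unless indicated otherwise, "summary statistics will be reported for observed data only and missing data will not be imputed".

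**The concern.** A percent change needs a baseline above zero. On the symptom scales zero is the best score and means that none of the scale's symptoms is present. Patients at zero can only stay there or worsen, so a row that omits them omits every case in which a symptom newly appears. Those who remain all have the symptom at baseline and have room to improve or to regress towards the mean. The C3D1-to-C5D1 row has the same gap for anyone at zero at C3D1.

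This matters because HR-QoL and symptom response is a secondary endpoint (Protocol 3.2.2), and because several commonly reported drug-related events in Protocol 1.4.3.1 (fatigue, nausea, vomiting, diarrhea, constipation, decreased appetite) correspond to symptom scales in Table 9. Substudies 1, 3 and 5 are single-arm and the Substudy 4 cohorts are non-comparative, so there is no control group against which an artefact would show up. Two adjacent rows could disagree in sign, on different sets of patients.

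**Working it through.** **1. Score range.** SAP 6.6.3 gives S = ((RS - 1)/range) x 100 for symptom scales, with range 3 from Table 9. For RS = 1, 2, 3, 4 this gives S = 0, 33.3, 66.7, 100. This reproduces the SAP's stated 0-100 range and confirms that a patient answering not at all throughout scores 0.

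**2. Percent change.** 100 x (follow-up - baseline)/baseline is undefined at baseline 0. Above zero it is asymmetric: 33.3 to 66.7 is +100%, and 66.7 to 33.3 is -50%. If equal numbers of patients make these two moves, the mean absolute change is 0 and the mean percent change is (100 - 50)/2 = +25%.

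**3. Worked example.** The size is 26, the planned size of Substudy 5. The scores are assumed: one single-item scale, 16 patients at 0 and 10 at 33.3.
- (a) Five of the 16 rise to 33.3 and five of the 10 fall to 0. Mean absolute change = (5 - 5) x 33.3/26 = 0.0 (N = 26). Mean percent change = (5 x -100% + 5 x 0%)/10 = -50% (N = 10).
- (b) Eight of the 16 rise and five of the 10 fall. Mean absolute change = (8 - 5) x 33.3/26 = +3.8, a worsening (N = 26). Mean percent change is still -50% (N = 10).

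**4. Range under assumed distributions.** The documents give no baseline symptom distribution, so the share at zero and the correlation are varied. Baseline and follow-up are correlated standard normal variables (correlation 0.4, 0.6, 0.8), cut at fixed baseline percentiles into 0/33/67/100. The cuts are 65/87/96, 50/80/95, 30/70/90 and 15/55/85. The three-item scale uses items with loading 0.8 on the same latent variable and the first three sets of cuts, which put 45%, 29% and 13% at zero on the scale. Percent change is averaged over patients with baseline above 0.

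Mean percent change with no true change:

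| Scale | Share at zero | Mean percent change |
|---|---|---|
| Single item | 65% | -19% to -39% |
| Single item | 50% | -13% to -27% |
| Single item | 30% | -5% to -10% |
| Single item | 15% | +0.5% to +2% |
| Three items | 45% | -5% to -2% |
| Three items | 29% | +6% to +10% |
| Three items | 13% | +12% to about +22% |

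**5. With true worsening** (follow-up shifted by 0.3 SD):
- Single item, 65% at zero, about 7.5 points worse: -17%, -4% and +11% at correlations 0.4, 0.6 and 0.8.
- Single item, 50% at zero, about 8 points worse: about -5% at correlation 0.4, positive at 0.6 and 0.8.
- Single item, 30% at zero, about 9 points worse: about +12% or more at every correlation.
- Three items, 45% at zero, about 6 points worse: about +26% or more.

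In these simulations, apparent improvement despite real worsening occurs only with a high share at zero and a modest correlation.

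**The case against.** A reader might infer that the percent-change row is biased towards benefit. The documents do not support that. They give no baseline distribution, and the sign of the distortion depends on it. With few patients at zero, or on a multi-item scale such as fatigue, low non-zero baselines generate large positive ratios and the row shows apparent worsening when nothing has changed. What stands is that the row can mislead either way.

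A reader might also infer that treatment-emergent symptoms would go unseen. They would not. The same summary reports the score and the absolute change. SAP 6.1.1 requires the number of observations for continuous variables, so a smaller N in the percent-change row would be visible. Adverse events are tabulated by preferred term under SAP 6.4.1. Protocol 8.3.8 describes the PRO analysis as primarily descriptive, the stage decisions rest on objective response by central review, and the minimally important difference methods in SAP 6.6.1 use absolute change. This limits the impact, and that part of the objection stands.

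Finally, the SAP does not say that zero-baseline patients are excluded. That follows from the arithmetic and from 6.1.4, and the table shells are in a separate document that might contain a convention. This does not rescue the plan: any convention would be a choice that the SAP has not stated.

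**Conclusion.** The concern holds as a flaw in a stated summary, with limited impact. By the SAP's own formula, percent change is undefined for symptom-free patients on the nine symptom scales and items. Under the observed-data rule the row loses them and every new onset from zero. For the patients left, the mean ratio is unstable and can contradict the absolute change in either direction.

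The size cannot be fixed from the documents. With no true change and correlations of 0.4 to 0.8, the assumed scenarios run from about -39% (single item, 65% at zero) to about +22% (three items, 13% at zero). These figures rest on the latent-normal model, the cut points and the item loading chosen here. A claim of systematic bias towards benefit is not supported, and no hypothesis test or stage decision depends on this row.

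**What to change.** In SAP 6.6.3, drop percent change, both from baseline and from C3D1 to C5D1, for the symptom scales and items. Keep the score and the absolute change, with N, for all patients with both assessments, including those at zero. A table of patients improved, unchanged or worse that includes those at baseline 0 would show onsets directly, but it is optional and would need a stated definition of each category.

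The cost is a change of SAP wording and the matching table shells. It needs no new data or procedures, and without the optional table there are fewer outputs.

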The FACT-BI is instrument which was developed for patients with bladder cancer. It contains 40 items and consists of the five subscales: physical well-being (PWB), functional well-being (FWB), emotional well-being (EWB), social well-being (SWB) and an additional scale specific to bladder cancer. In addition, the PWB, FWB, EWB, and SWB subscales can be summed to form the FACTGeneral (FACT-G) score and the FACT-BL total score (FACT-G and the bladder cancer specific scale). The items are scored on a 4-point scale (0=not at all, 1=a little bit, 2= somewhat, 3=quite a bit, 4 = very much) ([Karvinen 2007](#)).

The EQ-5D (5L) is a standardized instrument for use as a measure of health outcome. The EQ-5D will provide data for use in economic models and analyses including developing health utilities or QALYs. The five health state dimensions in this instrument include the following: mobility, self-care, usual activities, pain/discomfort, and anxiety/depression. Each dimension is rated on a five-point scale from 1 (no problem) to 5 (extreme problem). The EQ-5D also includes a graded (0 to 100) vertical VAS on which the patient rates his or her general state of health at the time of the assessment.

The Health Transition Index/G-SET is a single item and will be used as an external anchor to determine the minimal important difference of the EQ-5D visual analogue scale, EORTC QLQ-C30 scales and FACT-BI scales. It will be administered twice during the study following the recent protocol by the EORTC Quality of Life Group ([Musoro 2018](#)) for evaluating the minimal important difference. The SET will be provided after 6 weeks (at C3D1) and 12 weeks (at C5D1). The SET is a patient-rated change in health between two time periods using a five point ordinal scale (1=much better now than six weeks ago; 2=somewhat better now than six weeks ago; 3=about the same as six weeks ago; 4=somewhat worse now than six weeks ago; 5=much worse now than six weeks ago, the recall period was adapted compared to the original item) ([Ware 2002](#), [Lloyd 2014](#)).

The HR-QoL questionnaires will be provided to the patients to complete prior to being evaluated by the physician on D1 of every cycle, and at the End of Treatment visit.

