8.3.8 PRO analysis

PRO scores from the EORTC QLQ-C30, FACT-BI and EQ-5D instruments will be analyzed primarily using descriptive analysis.

The minimal important difference of the EQ-5D visual analogue scale, EORTC QLQ-C30 scales and FACT-BI scales will be determined using the Health Transition Index/G-SET as an external anchor.

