2.2. Secondary Objectives

- To evaluate the efficacy of the study drugs as measured by ORR (Substudy 2), disease control rate (DCR), duration of response (DOR), progression-free survival (PFS) and overall survival (OS)
- To assess the safety and tolerability of the study drugs
- To characterise the PK profile of derazantinib 200 mg BID (and, if applicable, derazantinib metabolites) as monotherapy (Substudy 5) and in combination with atezolizumab (Substudy 3).
- To evaluate changes, and assess the minimally important difference, in health-related quality of life (HR-QoL) and symptom response from baseline using the EORTC QLQ C30, FACT-BI, and EQ-5D (5L) visual analogue scale (VAS), and Health Transition Index/G-SET.

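### SAP 6.6.3 restricts the QLQ-C30 minimally important difference to five of 15 scales without declaring it, and SAP 6.6.4 uses the same restriction for FACT-Bl, where the term is undefined

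*SAP*

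**What the plan says.** Protocol 8.3.8 sets the scope of the MID analysis: "The minimal important difference of the EQ-5D visual analogue scale, EORTC QLQ-C30 scales and FACT-BI scales will be determined using the Health Transition Index/G-SET". Protocol 1.4.2 and 5.3.6 describe the same scope, and none of the three limits it to a group of scales. The secondary objective in Protocol 2.2 is "To evaluate changes, and assess the minimally important difference, in health-related quality of life (HR-QoL) and symptom response from baseline by cohort", and SAP 2.2 keeps the symptom part: "assess the minimally important difference, in health-related quality of life (HR-QoL) and symptom response from baseline".

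SAP 6.6.1 gives two estimation methods (mean change and linear regression) under a general opening: "For each assessment the minimally important difference (MID) in a score at C3D1 and C5D1 will be determined". It does not list the scales.

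The instrument sections do:

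- **EQ-5D (SAP 6.6.2):** "The minimally important change from baseline at C3D1 and change from C3D1 at C5D1 will be determined using the two methods", with no restriction.
- **QLQ-C30 (SAP 6.6.3):** "For each of the functional scales, the minimally important change from baseline at C3D1 and change from C3D1 at C5D1 will be determined". The same paragraph summarizes every scale descriptively.
- **FACT-Bl (SAP 6.6.4):** the same restricted sentence, again after a descriptive rule that covers every subscale and both totals.

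SAP 6.8, on changes to protocol-planned methods, names only the dropped inverse-probability-of-censoring-weighted analysis.

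**The concern.** The MID wording in two SAP sections is narrower than the protocol's and narrower than the descriptive rule beside it. A programmer who follows SAP 6.6.3 would produce no QLQ-C30 MID for any symptom scale or for global health status/QoL. The MID part of the symptom-response objective would then go unanswered for that instrument, and observed symptom changes could not be set against a threshold estimated in this trial. For FACT-Bl the programmer would have to guess what the phrase covers. If the scales are chosen after the data are in, the choice is post hoc.

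**Working it through.** No design figure such as power or alpha enters this point. The check compares scope and counts scales.

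**QLQ-C30 (SAP 6.6.3, Table 9).** The table has three labelled groups:

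- Global health status/QoL: 1
- Functional scales (PF, RF, EF, CF, SF): 5
- Symptom scales/items: 3 multi-item scales + 6 single items = 9

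Total: 1 + 5 + 9 = 15. An MID is specified for 5, so 15 − 5 = 10 have none. The scoring formulas under the table use the same split (one for functional scales, another for the rest), so the term has a fixed meaning here.

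**FACT-Bl (SAP 6.6.4, Table 10).** The scores are 5 subscales + FACT-G + FACT-Bl total = 7. None is grouped as functional scales, so the coverage depends on the reading:

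| Reading of the phrase | Scores with an MID | Scores without |
|---|---|---|
| Functional Well-Being only (literal) | 1 | 7 − 1 = 6 |
| The four well-being subscales | 4 | 7 − 4 = 3 (bladder subscale and both totals) |
| All five subscales | 5 | 7 − 5 = 2 (both totals) |

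**Does the general sentence in SAP 6.6.1 rescue the omitted scales?** It applies to each assessment but names no scales; the instrument sections do that. If it were meant to govern, the SAP would contradict itself and would still need correcting.

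**Direction of change.** This matters once symptom scales are added. Take a single item with range 3 and a raw score moving from 3 to 2.

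- Functional formula, S = (1 − (RS − 1)/range) × 100: from (1 − 2/3) × 100 = 33.3 to (1 − 1/3) × 100 = 66.7, a change of +33.3.
- Symptom formula, S = ((RS − 1)/range) × 100: from 66.7 to 33.3, a change of −33.3.

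The symptom change is an improvement with a negative sign. SAP 6.6.1 refers to a mean absolute change and does not say how sign is handled.

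**Data availability.** Protocol 5.3.6 has the questionnaires completed on Day 1 of every cycle and at end of treatment. The G-SET is given only at C3D1 and C5D1. The two intervals in the SAP (baseline to C3D1, C3D1 to C5D1) therefore already have both scores and anchor.

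**The case against.** Several points on the other side are sound.

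- The protocol says scales, not all scales, and Protocol 8 leaves analysis detail to the SAP. That leaves room for a deliberate narrowing, but SAP 6.8 is where a narrowing would be declared, and it is silent. No reason appears elsewhere in the SAP.
- A reader might infer that almost all of FACT-Bl loses its MID. That follows only from the most literal reading. A plural phrase fits poorly with a single subscale, and the sentence may simply have been carried over from the QLQ-C30 section. What the text supports is an undefined term, with 2 to 6 of 7 scores affected.
- A reader might infer that the SAP gives MIDs only to functional scales throughout, or drops symptom response altogether. Neither holds. The EQ-5D MID has no such limit, and every QLQ-C30 scale and FACT-Bl score is still summarized with change from baseline. The secondary endpoint in Protocol 3.2.2 concerns those changes and does not name the MID.
- A reader might infer that the scale nearest the anchor is left without an MID. Global health status/QoL is close to a question about health compared with six weeks ago, but the EQ-5D VAS, a rating of general health, is at least as close and keeps its MID.
- No analysis in SAP 6.6 uses an MID as a responder or deterioration threshold, so no other planned result changes.
- A single global-health anchor may track items such as constipation or financial difficulties poorly. This is a fair caution about interpretation. SAP 6.6.1 already allows an MID to be called doubtful when the no-change group resembles a small-change group.

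**Conclusion.** The point stands for the QLQ-C30: 10 of 15 scales get no MID under SAP 6.6.3, against an unrestricted protocol plan and an objective that includes symptom response, and the SAP does not declare the difference. This rests on taking the functional scales as Table 9 defines them and the protocol's unqualified mention of scales as covering the instrument. For FACT-Bl the defect is an undefined term, and the loss cannot be fixed more closely than 2 to 6 of 7 scores.

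The consequence is confined to a secondary, descriptive patient-reported objective. Response-rate testing, safety analysis and sample size are untouched. It should still be corrected, because the rule as written leaves part of a stated objective unanswered and the repair is small.

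**What to change.** - **SAP 6.6.3:** specify the MID for global health status/QoL, each functional scale and each symptom scale/item. State that a decrease on a symptom scale is improvement, and make clear in 6.6.1 that signed changes are used. QLQ-C30 coverage goes from 5 to 15 of 15.
- **SAP 6.6.4:** specify the MID for the five subscales, FACT-G and the FACT-Bl total. Coverage becomes 7 of 7.
- **Weak anchoring:** flag MIDs for items that follow the global anchor poorly under the existing provision for doubtful estimates in 6.6.1.
- **If the narrowing is intended:** list it with a reason in SAP 6.8, and still define the FACT-Bl scales meant.

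No new data or visits are needed. The cost is two rewritten sentences, a sign convention and additional output rows. For the QLQ-C30 that is 10 more scales, each with 2 intervals × 2 directions × 2 methods = 8 estimates, or 80 more per cohort. The output shells are in a separate document, so the programming effort cannot be judged from the protocol and SAP.
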